PDMP	Prescription Drug Monitoring Program
PE	Pulmonary Embolism
PI	Principal Investigator

1 ABBREVIATIONS USED IN THE PROTOCOL

PI Name: [name] Research Protocol: July 25, 2019 Version 1.2 (03/17/20)

Abbreviation	Term
PT	Physical Therapy
RA	Rheumatoid Arthritis
RCT	Randomized Controlled Trial
SAE	Serious adverse event
SOC	Standard of Care
TKA	Total Knee Arthroplasty
VR	Virtual Reality
VR-12	Veterans Rand 12 Item Health Survey

PI Name: [name] Research Protocol: July 25, 2019 Version 1.2 (03/17/20)

2 ABSTRACT

In 2016, the American Pain Society published guidelines on the management of postoperative pain based on a systematic review of the various interventions and management strategies. A key recommendation was that "clinicians offer multimodal analgesia, or the use of a variety of analgesic medications and techniques combined with non-pharmacological interventions, for the treatment of postoperative pain in children and adults (strong recommendations, high-quality evidence). [1]

According to the August 21, 2013 Journal of Bone and Joint Surgery, one half of patients now receiving knee replacements are under 65 and demand for Total Knee Arthroplasty (TKA) is expected to exceed 3.5 million procedures per year by 2030. [2]

Multimodal treatment plans provide an advantage for acute postoperative pain. Multi-modal pain treatment can also be improved by discharge to home and performing activities of daily living, physical therapy treatment within 24 hours of discharge and weight bearing as tolerated. The use of virtual reality (VR) has been shown to be a safe and effective adjunctive therapy for pain and low risk opioid sparing treatment. [3]

We propose to study the effects of a VR-based pain management program, RelieVRx, in acute postoperative pain after orthopedic TKA surgery in 100 patients (50 patients in the standard of care plus RelieVRx test group and 50 patients in the standard of care control group). RelieVRx is a virtual reality therapy intended as adjunctive treatment for acute surgical pain. RelieVRx is intended to be a prescription therapy for the reduction and/or elimination of opiate use in patients suffering from acute surgical pain. Patients will be randomized to one of the two groups after study enrollment, and patients in the test arm will be educated about the device preoperatively to facilitate its use in the acute postoperative period. The goals of VR will be presented in the context of an alternate to opioids for pain control. Subjects will be assured they will receive SOC analgesic management in addition to the VR headsets.

PI Name: [name] Research Protocol: July 25, 2019 Version 1.2 (03/17/20)

3 BACKGROUND AND SIGNIFICANCE

Pain following orthopedic injuries and operations, including over 6.6 million orthopedic surgeries anticipated in 2020 [1], is significant and sustained during the entire period of recovery. This recovery period can be quite long depending on the specific orthopedic operation and underlying disease or comorbidities. Treatment and management of this pain is traditionally based primarily around utilizing pharmacological management.

Opiates are commonly prescribed as part of post-operative pain management which can lead to Opioid Use Disorder (OUD). These agents can yield both inconsistent and sub-optimal results [4] and greatly increase the risk of the patient developing an opioid addiction or OUD. Data from the U.S. Center for Disease Control (CDC) revealed that even a single day of opioid therapy can predict up to a 6% increase in the risk of the patient developing a dependency within a year [5].

Two retrospective cohort studies found opioid therapy prescribed for acute pain was associated with greater likelihood of long-term use. One study evaluated opioid-naïve patients who had undergone low-risk surgery, such as cataract surgery and varicose vein stripping [5]. Use of opioids within 7 days of surgery was associated with increased risk for use at 1 year. The second study found that among patients with a workers' compensation claim for acute low back pain, compared to patients who did not receive opioids early after injury (defined as use within 15 days following onset of pain), patients who did receive early opioids had an increased likelihood of receiving five or more opioid prescriptions 30–730 days following onset that increased with greater early exposure [6]. While new opioid guidelines, such as the 2016 CDC opioid guidelines [7] or 2018 Centers for Medicare and Medicaid Services (CMS) rules [8], are limiting the number of opioids available to opioid "naïve" patients to an initial 7-day supply, regardless of dose, a lack of alternative pain management solutions exist.

Unlike VR, opioids have a significant adverse event profile that includes hypotension, respiratory depression or arrest, aspiration, or vomiting. Although both risks and costs are often considered manageable, it is imperative to devise alternatives to address pain after surgery that are cost-effective and improve the risk benefit profile well above standard of care.

It is hypothesized that the anterior cingulate cortex (ACC) plays a significant role in both the detection and response to pain. Indeed, functional MRI (fMRI) studies with VR have shown diminished pain-related brain activity in five regions associated with pain sensation. Regarding emotion, it has been demonstrated that emotions can modulate pain by activation/deactivation of the amygdala. Negative emotions, such as anxiety and depression, can facilitate pain while positive emotions can inhibit the pain-control pathway.

PI Name: [name] Research Protocol: July 25, 2019 Version 1.2 (03/17/20)

To reduce addiction, low risk, non-opioid pain analgesics are in great need and virtual reality (VR) shows great promise as a solution. Therapeutic VR has emerged as an effective, non-pharmacological treatment modality for pain [4]. Users of VR wear a pair of goggles with a close-proximity screen that creates a sensation of being transported into immersive, three-dimensional worlds. A hypothesis for the mechanism of action for VR suggests that by stimulating the visual cortex while simultaneously engaging other senses, VR is able to limit the user's processing of pain signals [4].

4 SPECIFIC AIMS

4.1 SPECIFIC AIM 1

Among standard of care (SOC) plus RelieVRx (SOC+RelieVRx) group, compare pain scores before and after use of RelieVRx. *Hypothesis: Acute postoperative pain scores will decrease by at least 20% or 2 points on a 0-10 Numerical Pain Rating Scale (NPRS) after each use of RelieVRx*.

4.2 SPECIFIC AIM 2

Compare pain scores between the SOC group and SOC+RelieVRx group. *Hypothesis: Cumulative pain scores will be comparable among the SOC+RelieVRx group and SOC group.*

4.3 SPECIFIC AIM 3

Compare opioid use between the SOC group and SOC+RelieVRx group. *Hypothesis: Opioid consumption will be reduced by at least 20% over a 90-day postoperative period in the SOC+RelieVRx group compared to the SOC group.*

5 STUDY DESIGN

5.1 **Description**

This is a prospective, randomized, controlled study of the appliedVR RelieVRx pain management solution in subjects undergoing Total Knee Arthroplasty (TKA).

Patients at each study site will be randomized by computer 1:1 to either the SOC (control) group or the SOC+RelieVRx (test) group. The SOC+RelieVRx group will receive education and hands-on experience with the VR headset and RelieVRx pain management solution at a routine preoperative patient education class or during the history and physical encounter visit through a predetermined script to make the patient feel comfortable using the device on their own. The goals of VR will be presented in the context of an alternate method of pain control to opioids. Subjects will be assured they will receive SOC analgesic management in addition to the headsets. The participating surgeons and anesthesiologists at Geisinger Medical Center will

PI Name: [name] Research Protocol: July 25, 2019 Version 1.2 (03/17/20)

adhere to a standardized medication regimen for anesthesia and pain relief prescriptions in order to minimize confounding between the groups due to differences in pain medication treatment plans.

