5.2 STUDY POPULATION

5.2.1 Approximate Number of Subjects

Approximately 100 Geisinger subjects who have TKA surgery at Geisinger will participate in this study (50 will be in the SOC group and 50 will be in the SOC+RelieVRx group).

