5.6.1 Sample Size Considerations

This study has been designed with consideration for power requirements of both primary and secondary endpoint evaluations, as well as requirements for a noninferiority trial evaluating the overall effectiveness of RelieVRx as an opioid-sparing product.

Primary Endpoints

Preliminary data collected at Geisinger Medical Center (Danville, PA) between March 2017 and December 2018 from 1,052 patients who underwent total joint arthroplasty showed an average postoperative pain score of 8.50 following the procedure, and 6.16 on day 2 (SD = 2.0; change d = 1.2, or a 28% pain reduction) under SOC.

To assess the acute effectiveness endpoint of 20% average reduction in pain scores, each onesample *t*-test only requires data from 13 patients to demonstrate a significant difference from zero, assuming 20% attrition, a Type I error rate of 5% and a Type II error rate of 20% (i.e., 80%

PI Name: [name] Research Protocol: July 25, 2019 Version 1.2 (03/17/20) power). In order to observe significance of a lower threshold (e.g., a 10% reduction in pain level on average), data from **43 patients using VR** will be required, assuming 20% attrition, a Type I error of rate 5% and 80% power.

To assess the overall effectiveness for reducing opioid usage by at least 20%, this study assumes an average MME per day of 12.5mg (SD = 3) across all users, although continuous opioid users may report averages higher than 50mg/day. Observing a 20% relative reduction in opioid usage in the SOC+VR group compared to SOC (2.5mg) will require **64 patients total (32 per group)**, assuming 25% attrition, a Type I error rate of 5% and 80% power. If interim data analysis reveals unexpectedly high variability in opioid consumption, a revised power calculation based on new data may increase data collection requirements to address this question.

Secondary Endpoint

Using aforementioned preliminary data, two patients groups were created with simulated VAS-%AUC data (with day 14 VAS means of 6.16 and 4.93, SD = 2.0; or, a 20% greater reduction at day 14) corresponding to a 7% difference in VAS-%AUC (0.86 versus 0.79; SD = 0.1; difference d = 0.7). Assuming 25% attrition, the study will require **92 patients total** (**46 per group**). Data from at least 68 patients is needed to observe a statistically significant VAS-%AUC difference between SOC and SOC+VR of 7% in an unpaired *t*-test, with a Type I error rate of 5% and 80% power.

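### The opioid comparison ignores preoperative opioid use in both allocation and primary test, so a few continuous users could shift the result by the 2.5 mg/day sought

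*Combined protocol and SAP*

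**What the plan says.** - **Allocation (5.1 Description).** "Patients at each study site will be randomized by computer 1:1 to either the SOC (control) group or the SOC+RelieVRx (test) group". No stratification factor, block scheme or minimisation is described there or elsewhere.
- **Eligibility (5.2.3 Exclusion Criteria).** Chronic pain syndrome and a substance abuse disorder within the past year are excluded. Prescribed opioid use before surgery is not.
- **Planning assumption (5.6.1 Sample Size Considerations).** "this study assumes an average MME per day of 12.5mg (SD = 3) across all users", followed in the same sentence by "although continuous opioid users may report averages higher than 50mg/day". The target is a 20% reduction, 2.5 mg/day, and the stated requirement is "64 patients total (32 per group"), "assuming 25% attrition, a Type I error rate of 5% and 80% power". Planned enrolment in 5.2.1 is larger: "50 will be in the SOC group and 50 will be in the SOC+RelieVRx group".
- **Analysis (5.6 Study Endpoints and Statistical Plan).** Average MME per day is compared by an unpaired t-test or a Wilcoxon rank-sum test. Preoperative opioid use appears only among the covariates of additional mixed models of usage over time.
- **Data available.** The 5.5.1 events table records opioid use before surgery, and 5.5 provides for PDMP queries.

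**The concern.** A continuous user at 50 mg/day uses four times the planned mean (50 / 12.5 = 4), and the gap of 37.5 mg/day is fifteen times the difference sought (37.5 / 2.5 = 15). In arms of this size, a handful of such patients falling unevenly can move the difference in means by as much as the device is expected to. Even when they fall evenly, they inflate the variance that the t-test works against. The plan itself treats preoperative use as prognostic, since it lists it as a covariate, but uses it neither in allocation nor in the primary comparison. Opioid reduction is one of two primary endpoints, and section 8 intends the data for a de novo submission. A result that a few patients' allocation could produce or erase would be hard to interpret.

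**Working it through.** **Inputs from 5.6.1 and 5.2.1.** Mean 12.5 mg/day, SD 3, difference 2.5 mg/day, alpha 5% (taken as two-sided), power 80%, attrition 25%, 50 enrolled per arm. Continuous users are set at 50 mg/day, a gap of 50 − 12.5 = 37.5 mg/day.

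**Assumed.** Prevalence of continuous users, which the documents do not give; 1% to 10% is shown. Continuous users are taken to be largely identifiable before surgery.

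**1. The plan's own figure.** d = 2.5 / 3 = 0.833. A two-sided two-sample t-test at 80% power needs 23.6, so 24 per arm. 24 / (1 − 0.25) = 32 per arm, 64 in total. The stated figure reproduces exactly, given SD 3.

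**2. Is SD 3 compatible with such users?** Their contribution to the variance is 37.5² × p(1 − p). This equals 3² = 9 at p of about 0.64%, so any higher prevalence exceeds the assumed variance without help from other patients. At p = 5%, with SD 3 among the rest, the SD is √(9 + 37.5² × 0.05 × 0.95) = 8.7.

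**3. Imbalance worth the whole effect.** One net extra user shifts the arm difference by 37.5 / n.
- n = 37 (50 × 0.75 = 37.5, rounded down): 1.01 mg/day each; 2.5 / 1.01 = 2.5, so 3 patients.
- n = 50: 0.75 mg/day each; 2.5 / 0.75 = 3.3, so 4 patients.

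**4. How often that happens.** The count in each arm is Binomial(n, p), independently. The table gives the probability that the counts differ by at least 3 (n = 37) or 4 (n = 50), in either direction.

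| Assumed prevalence | 37 per arm | 50 per arm |
|---|---|---|
| 1% | 1% | 0.2% |
| 2% | 4% | 1.6% |
| 5% | 17% | 10% |
| 10% | 33% | 24% |

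**5. Power for 2.5 mg/day at 37 per arm.** Simulation with Normal(12.5, SD 3) for each patient, plus 37.5 for a continuous user, less 2.5 for every patient in the test arm.

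| Assumed prevalence | Unadjusted t-test | Adjusted for heavy baseline use |
|---|---|---|
| 2% | 51% | 93–95% |
| 5% | 27% | 93–95% |
| 10% | 16% | 93–95% |

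The Wilcoxon test has about 87% at 5% and 79% at 10%. At 50 per arm, for 5% and 10% prevalence, the t-test has 33% and 19%, Wilcoxon 95% and 89%, and the adjusted model 98% to 99%. With no true effect, the t-test rejected in 4% to 5% of trials at prevalences of 5% to 20%.

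**6. What a yes/no split would do.** Suppose 20% to 40% of patients have some preoperative use (assumed) and heavy users are a subset. The overall mean is held at 12.5, so the gap is 37.5 / (1 − p): 39.5 mg/day at 5% and 41.7 at 10%. Without stratification, at 50 per arm, the SD of the chance difference is 39.5 × √(2 × 0.05 × 0.95 / 50) = 1.7 mg/day at 5%, and 41.7 × √(2 × 0.10 × 0.90 / 50) = 2.5 at 10%. Yes/no stratification in blocks of 4 leaves about 1.6 to 1.7 and 1.9 to 2.3. Under the model of step 5, a yes/no covariate gives only about 18% to 38% power across the 5% and 10% cases at 37 and 50 per arm.

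**The case against.** **The exposure may be small.** Prevalence is unknown. The exclusions for chronic pain syndrome and recent substance abuse disorder, together with the opioid-avoiding care pathway in 5.5, point to a low figure. At 1% an imbalance of this size is rare. This stands, and it is why the result is given as a range. But it was the sponsor who wrote these users into the sample-size section.

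**Continuous is not defined as preoperative.** The term in 5.6.1 could also cover use that persists after surgery, which no baseline variable captures fully. This stands: the link is an inference, and the adjusted power figures are a best case.

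**The plan already mitigates.** It does, in part. The Wilcoxon test is far less affected, but it is only an alternative to the t-test and does not estimate the difference in mean MME/day. The mixed models are additional, and their covariates include postoperative analgesics and dosage changes, which treatment may affect. The power review in 5.6.1 may add patients but does not balance the arms or adjust the comparison.

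**Stronger readings that a reader might infer.** One is that the endpoint is biased, or its false-positive rate inflated. Randomisation prevents that, and the simulated error rate stayed at or below 5%. Another is that stratification is ruled out. The protocol is silent on it, and allocation at each site may already imply separate lists by site. A third is that stratifying on any preoperative use would nearly remove the imbalance. That needs every preoperative user to be a heavy user, which the documents do not say.

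**Conclusion.** The concern holds as a loss of precision and power in a primary endpoint, not as bias. The documents describe no stratification by preoperative opioid use, admit such patients, and leave the factor out of the primary opioid comparison, while expecting some patients at four times the planned mean or more.

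An imbalance worth the whole 2.5 mg/day is unlikely if continuous users are 1% to 2% of patients (0.2% to 4% of trials) and material at 5% to 10% (10% to 33%). The power loss matters even at 2%, where the unadjusted t-test falls to about half at 37 per arm.

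These figures rest on assumed prevalences, a 37.5 mg/day gap, SD 3 among other patients, the same 2.5 mg/day effect in every patient, and heavy use that is recognisable at baseline. If the Wilcoxon test were fixed as the primary test the power loss would be much smaller, but the plan does not fix it. The change is worth making because it uses information already collected.

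**What to change.** 1. **Section 5.6, the main change.** Make the primary opioid comparison a model adjusted for preoperative opioid use as a quantity: baseline MME/day from the pre-surgery record and the PDMP, captured before allocation. Do not include covariates measured after randomisation in this model. It can be adopted whatever the allocation scheme, and in the simulation adjustment recovered the power without stratification.
2. **Section 5.1, for patients not yet randomised.** Stratify by preoperative opioid use within site, in small permuted blocks, and include the stratum in the model. The investigators should define the boundary in advance so that it separates continuous users from occasional users and non-users. A plain yes/no split recovers little if many patients have occasional use.
3. **Section 5.6.1.** State the expected proportion of continuous users, say whether the term means use before surgery, and re-justify SD 3 in that light.

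**Cost.** One field in the randomisation program, one baseline variable derived from data already collected, and possibly sparse strata at a small site.

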5.3 RECRUITMENT

The primary and collaborating investigator(s) will identify potential subjects in their respective clinics that have elected to undergo primary TKA. These patients will also be pre-screened via manual chart review of their electronic health record (EHR) by the research team. Patients meeting the inclusion/exclusion criteria will be approached by an IRB approved study team member (e.g. primary and collaborating physicians, research project manager and/or project coordinator) during their orthopaedic clinic visit, orthopaedic health and physical, and/or Total Joint Class. Before asking for patient consent, the study will be explained in its entirety and the patient will have ample opportunity to ask any questions or express any reservations.

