5.6 STUDY ENDPOINTS AND STATISTICAL PLAN

This study will evaluate two primary endpoints – effectiveness of a single use of RelieVRx in the reduction of acute postoperative pain by 20%; and overall effectiveness of RelieVRx as an opioid-sparing intervention, where opioid and non-opioid consumption is reduced by at least 20% over a 90-day postoperative period in the SOC+VR group compared to the SOC group.

Acute effectiveness will be evaluated using NPRS data collected before and after each use of RelieVRx (up to 3 times per day) over the 14-day postoperative period. NPRS is measured on a scale of 0-10, with 0 being the least amount of pain and 10 being the most. Because pain levels will vary by time of day administered and are expected to peak in the first 24-72 hours postoperatively and drop afterward, acute effectiveness will be evaluated at all stages of recovery. The expected 20% reduction after single use will be scaled relative to the pre-use pain score [e.g. users reporting a pre-VR pain level of 8 would need to report post-VR pain levels of 6.4 (8 * 80%) on average; users reporting pre-VR pain of 5 would need to report pain levels of 4 post-VR, etc.]. Each SOC+VR patient will use VR up to 44 times over the 14-day recovery period, requiring linear mixed model analysis to assess acute changes in pain scores while accounting for stage of recovery and other covariates, such as age, preoperative health status and opioid use, and postoperative complications. For interim and final endpoint analyses, pain %change scores will be calculated for each use and averaged for each patient across the 72-hour acute postoperative period, the following week, after 10 days, and overall. These averages will be evaluated using one-sample unpaired *t*-tests (or the nonparametric one-sample Wilcoxon signed-rank test, as needed for non-normal data).

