Overall effectiveness will be evaluated by tracking daily opioid usage 90 days postoperatively in both SOC and SOC+VR groups. Average MMEs (Morphine Milligram Equivalents) per day will be compared using unpaired Student's *t*-test (or the nonparametric Wilcoxon rank-sum test) in interim and final endpoint analyses. In addition, changes in usage over time will be evaluated using linear mixed models (or nonlinear models, given data shape), accounting for variations in recovery time across patients and other covariates, such as other analgesic medications used postoperatively, preoperative opioid use, and dosage changes. A sub-analysis will compare usage in the 14-day acute postoperative recovery period.

The secondary endpoint of this study is a comparison of the cumulative experience of pain over the 14-day acute postoperative period between SOC and SOC+VR groups. In order to quantify pain that fluctuates over time, NPRS pain scores will be plotted for each patient over the acute postoperative period, using straight-line interpolation between measurements. This approach will allow for incorporation of all data collected (even if some patients participate more than others), and will avoid overemphasis on a single outcome measure (e.g. pain on day 14). Percent-areaunder-the-curve (VAS-%AUC) measurement will be calculated for each patient by adding the

PI Name: [name] Research Protocol: July 25, 2019 Version 1.2 (03/17/20)

areas of consecutive trapezoids defined by time on the x-axis and pain level measurements on the y-axis (e.g. 100% would indicate pain scores of 10 across the entire time period; 50% would indicate a linear reduction from 10 to 0 over the same time period). In interim and final endpoint analyses, NPRS-%AUC accumulated to date will be compared between groups using an unpaired Student's *t*-test (or nonparametric equivalent). In addition, linear mixed models will be used to compare cumulative pain between SOC and SOC+VR groups over time, as well as pain experienced in the inpatient postsurgical period and following days.

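### Section 5.1 randomises 1:1 at each study site, but the between-group tests are unadjusted and no model names site; if allocation is balanced within several sites, those tests are mildly conservative

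*Combined protocol and SAP*

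**What the plan says.** Section 5.1 places randomisation at site level: "Patients at each study site will be randomized by computer 1:1". It mentions no strata, blocks or separate lists, and the number of sites is not given. Other sections point both ways on whether there is more than one:

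- Section 5.3 says investigators "will identify potential subjects in their respective clinics", and section 5.5 also refers to study clinics in the plural.
- Section 5.2.1 says "Approximately 100 Geisinger subjects who have TKA surgery at Geisinger will participate in this study". The standardised medication regimen in section 5.1 names one centre only: "The participating surgeons and anesthesiologists at Geisinger Medical Center will" follow it.

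The analyses in section 5.6 are:

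- Opioid primary endpoint: "Average MMEs (Morphine Milligram Equivalents) per day will be compared using unpaired Student's" t-test, or a Wilcoxon rank-sum test.
- Secondary endpoint (NPRS-%AUC): unpaired t-test or its nonparametric equivalent.
- Acute-pain primary endpoint: "These averages will be evaluated using one-sample unpaired" t-tests, within the VR arm only.
- Mixed models: for acute pain, "other covariates, such as age, preoperative health status and opioid use, and postoperative complications"; for opioids, "other covariates, such as other analgesic medications used postoperatively, preoperative opioid use, and dosage changes". Site is in neither list, but both lists are illustrative rather than closed.

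**The concern.** When arms are balanced within site, the design removes site differences from the treatment contrast. A two-sample test that ignores site still counts those differences as error, so the reported standard error exceeds the true one, the test rejects too rarely under the null, and some power is given up. Opioid use is an outcome for which prescribing habits could differ between sites. Section 5.1 is itself concerned about confounding from differing pain-medication plans, though it names one centre when it standardises the regimen.

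There is also a pre-specification issue. With open covariate lists and no statement on stratification, whether site enters a model could be settled after the data are seen.

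**Working it through.** **Inputs from section 5.6.1.** Opioids: difference 2.5 mg MME/day, SD 3, so d = 2.5/3 = 0.833. NPRS-%AUC: 0.86 versus 0.79, SD 0.1, so d = 0.7. Both use alpha 0.05, 80% power and 25% attrition. Section 5.2.1 plans 50 per arm.

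**The plan's own figures.** A two-sample t-test at two-sided 0.05 with 80% power and d = 0.833 needs 23.6, so 24 per arm; 24/0.75 = 32 per arm, 64 in total, as stated. For d = 0.7 the solution is 33.02, so 34 per arm (68 evaluable); 34/0.75 = 45.3, so 46 per arm, 92 in total, as stated. Neither calculation has a site term.

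**Assumption.** Let ρ be the share of outcome variance due to site. The documents do not give it; 0 to 0.15 is shown.

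**Formulas, for allocation balanced within site (normal approximation).**

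- Reported SE / true SE = 1/√(1−ρ)
- True two-sided alpha of the unadjusted test = 2[1 − Φ(1.96/√(1−ρ))]
- With c = d√(n/2): unadjusted power = Φ((c − 1.96)/√(1−ρ)); site-adjusted power = Φ(c/√(1−ρ) − 1.96)

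The minimum evaluable sizes give c = 0.833 × √12 = 2.887 for opioids and c = 0.7 × √17 = 2.886 for %AUC, so the two endpoints have practically the same power there. After 25% attrition, 50 per arm leaves 37.5, taken as 37: c = 3.584 for opioids and 3.011 for %AUC.

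| ρ (assumed) | SE excess | True alpha | Minimum n (24 opioids, 34 %AUC): unadjusted / adjusted power | Opioids, n = 37 | %AUC, n = 37 |
|---|---|---|---|---|---|
| 0 | 0% | 0.050 | 82.3% / 82.3% | 94.8% / 94.8% | 85.3% / 85.3% |
| 0.05 | 2.6% | 0.044 | 82.9% / 84.2% | 95.2% / 95.7% | 86.0% / 87.1% |
| 0.10 | 5.4% | 0.039 | 83.6% / 86.1% | 95.7% / 96.5% | 86.6% / 88.8% |
| 0.15 | 8.5% | 0.034 | 84.3% / 87.9% | 96.1% / 97.3% | 87.3% / 90.4% |

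From ρ = 0.05 to 0.15 the power forgone is 1.3 to 3.7 points at the minimum sizes. At 37 per arm it is 0.5 to 1.2 points for opioids and 1.1 to 3.1 points for %AUC. The normal approximation runs slightly high: exact t-test power at ρ = 0 is 80.7% (24 per arm) and 81.2% (34 per arm).

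**Simulation check (opioids, N = 48, 3 or 4 equal sites, 8,000 runs per setting).**

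- *Balanced within site.* The unadjusted test's size was 0.034 to 0.038 at ρ = 0.10 to 0.20. With 4 sites, unadjusted and adjusted power were 80.1% and 79.9% at ρ = 0, 81.2% and 82.1% at ρ = 0.05, and 82.4% and 84.1% at ρ = 0.10.
- *Simple randomisation.* The unadjusted test kept its level (0.047 to 0.053). With 4 sites, adjusting for site moved power from 79.4% to 76.4% at ρ = 0, left it about level at ρ = 0.10 (81.9% and 82.2%), and raised it from 82.3% to 86.2% at ρ = 0.20.

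**The case against.** A reader might infer that standard errors will be too wide and that power is lost relative to the plan. The documents do not support that.

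- *Stratification is not documented.* Randomising 1:1 at each site is naturally read as allocation within site, but no blocks or per-site lists are mentioned. Under simple randomisation the unadjusted standard error is valid. This stands, and makes the point conditional.
- *Several sites are not established.* Geisinger is the only institution named, and plural clinics may describe where patients are found rather than where they are randomised. This also stands.
- *Site is unnamed, not excluded.* The mixed-model covariate lists are open, so it would be too strong to say that no analysis includes site. The t-tests and rank-sum tests, however, have no place for it.
- *Only one primary endpoint is involved.* The acute-pain endpoint is a one-sample test in the VR arm, which balance between arms cannot affect.
- *Site differences may be close to nil.* A standardised regimen and a common recovery programme in both arms plausibly shrink them. That is why the range starts at zero.
- *The error is in the safe direction.* There is no bias and no inflation of Type I error, and the unadjusted test's power under balanced allocation stays at or above 80%.

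What survives is that the plan describes randomisation by site, does not say how it works, and specifies between-group tests that do not reflect it.

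**Conclusion.** This is a minor point, conditional on more than one site, allocation balanced within site, and a site effect on the outcome. Where all three hold, the unadjusted tests of MME/day and NPRS-%AUC are mildly conservative, to the extent tabulated above for an assumed site share of up to 15%. The cost is efficiency forgone relative to a site-adjusted analysis, not a shortfall against the planned 80% power. If any of the three conditions fails, the unadjusted standard errors are sound. The documents settle none of them, so the number of sites and the form of allocation need to be stated.

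**What to change.** In section 5.1, state the number of sites and that allocation is stratified by site. In section 5.6, include site as a factor in the between-group opioid and NPRS-%AUC analyses: a linear model in place of the t-test, or a site-stratified rank-sum test if a nonparametric method is used. Name site as a covariate in the between-group mixed models too. The one-arm acute-pain test needs no change.

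If there is only one site, delete the words in section 5.1 that place randomisation at each site, and change nothing else.

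The cost is a few sentences of SAP text and a few degrees of freedom. If site turns out not to be prognostic there is a small power loss: negligible in the simulation with balanced allocation (80.1% to 79.9%), but about 3 points at N = 48 with 4 sites if allocation is not balanced within site. This is why the stratification should be stated along with the adjustment.
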